All IOP counselors will be trained in the Step where they are randomized to implement PARS. In this way, the study sites are “engaged” in the research as counselors on site will provide the study interventions. The agencies will be deferring human subjects review to the UW and have completed an Institutional Agreement for IRB Review (IAIR) with each site.

[name], who developed PARS, will provide all the training. To maximize the value to our community partners and assure a counselor trained in PARS is available on the day the PARS module is scheduled, all consenting counselors will be offered the opportunity to participate in the training so that someone can substitute if the designated PARS counselor is unavailable.

PARS counselor adherence will be evaluated at the first PARS administration by having an adherence coder sit in on the PARS session. Observation is the method requested by the agency treatment partners as least disruptive and most acceptable to clients. As adherence coders will have participant contact and be hearing the treatment session, they will complete any training on specific agency procedures regarding treatment observers with regard to client PHI so the adherence coders meet all agency standards. No client PHI will be collected as part of adherence coding – the focus is on the counselor’s level of adherence to PARS and not client identity nor comments.

Both Conditions:

Any additional treatments outside of the IOP program (e.g., mental health-oriented counseling, pharmacotherapy) will be available during all phases of the Stepped design. Washington State mandates self-help group attendance in addition to attendance of group and individual IOP sessions; this will also remain consistent throughout each site’s participation (regardless of when PARS is implemented at each site).

Client Participant Assessment Procedures:

Reminder – clinics are randomized at the clinic level. Clients and counselors have no choice in if they receive the intervention. This randomization effects clients and counselors regardless of whether they are study participants or not. As noted above, participants are informed about this in the consent form and we request waiver of consent for the non-participants.

Baseline Assessment

Will always occur one week prior to session intervention.

Will be conducted by in-person group administration. Assessments will be completed on paper or tablet computers. Expected to take 15-30 minutes.

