Note that for the Administrative Supplement, we are describing the PARS intervention to them but there is no trial of the intervention, *per se*.

5.2 Data variables. Describe the specific data you will obtain (including a description of the most sensitive items). If you would prefer, you may upload a list of the data variables to the **Supporting Documents** SmartForm instead of describing the variables below.

We will collect questionnaire data on REDCap on a tablet or paper (baseline) or online (follow-up). Follow-up interviews will be conducted by phone if so requested by a participant. The content of the questionnaires and description of most sensitive items are described below in Section 5.13.

Our goal is to attempt recruitment of all counselors at each site at each Step of the study. At Steps 2-6, the study therefore reaches out to the site's point of contact to determine if there are any counselors who have left or new counselors hired since the previous Step. New counselors can then be recruited. To prevent inadvertent re-recruitment of counselors who refused to participate at an earlier Step: we request to retain the names of counselors who refuse so that the research staff can provide a complete list of counselors from the previous Step to the site point of contact and clarify who refused so they won't be re-recruited.

We will also obtain the medical record for each participant for their treatment at the site that includes the IOP program and an ancillary services. This will allow us to determine how many IOP sessions they attended and whether they completed the program, what other services they received, what diagnoses and problems were identified for that client and whether they resolved during the course of treatment, and what their disposition plan was following the IOP program. If any of this information is not clear in the medical record, a research assistant will ask the counselor to clarify or add needed information verbally.

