PARS is a module designed for a single session of an IOP treatment program including a specified combination of didactic presentations and group discussions. PARS topics include: Goals and Objectives; Suicide Overview; Addiction and Suicide: A Strong Relationship; Suicide Myths and Facts; Suicide Risk Factors; Suicide Protective Factors; Common Triggers of Suicidal Thoughts and Behaviors; Warning Signs and

Guidelines for Preventing Addiction Related Suicide. The PowerPoint slides of the PARS curriculum (and also serving as the training materials) as well as the PARS adherence measure can be found in the Appendix.

The IOP counselor will administer PARS. PARS developer [name] will provide all training in PARS. In preparation for each site providing PARS, [name] will provide PARS training using the training model developed in the R21. [name] and [name] (Licensed Independent Clinical Social Worker and Research Scientist) will evaluate adherence to PARS by the community treatment counselor in a practice session to assure the counselor can provide PARS with fidelity. Based on the experience from our PARS R21, training will begin one month prior to implementation to assure sufficient time and practice. To maximize the value to our community partners and assure a counselor trained in PARS is available on the day of the PARS module, multiple counselors will participate in the training so that someone can substitute if the designated PARS counselor is unavailable. [name] and [name] will assure adherence of all study administration of PARS.

Both Conditions:

Any additional treatments outside of the IOP program (e.g., mental health-oriented counseling, pharmacotherapy) will be available during all phases of the stepped design. Washington State mandates self-help group attendance in addition to attendance of group and individual IOP sessions; this will also remain consistent throughout each site's participation (regardless of when PARS is implemented at each site). Documentation of all services received or referred to will be gathered from the program (with client consent).

Stepped Wedge Design

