This study will use a stepped wedge design as shown in Figure 1. This design is recommended for studies in which it is beneficial to randomize at the site rather than individual level.³⁵⁻³⁷ Such is the case in this study, as randomization at the individual level would not be feasible with our community partners, who are enrolling clients and placing them in groups based on many complex reasons including client schedules, IOP group schedules and openings, and a myriad of agency guidelines and regulations. Such a study would require conducting PARS and usual care in a research clinic setting—which is the opposite of our goal. PARS was developed in community settings and its effectiveness in those settings is key. Once it was determined that randomization would be at the site level, both clustered randomized and stepped wedge designs were considered.^{35,37-44} While both have benefits, the stepped wedge has the advantage of measuring dose-response (delay) effects. Furthermore, its primary disadvantage (that more assessment points were required)^{35,40,42} was not determined to be a problem for the research team or community partners, as participants would complete the same assessments regardless of stepped wedge or cluster randomization.

In the proposed study, there will be six steps. Steps will be 6 months each to assure sufficient time for all data collection to occur given that some IOP programs are as long as 12 weeks and sites will vary as to which session PARS replaces in their IOP curricula. In each of the six steps of the study, baseline assessments will be conducted the week before that selected session at that site. For instance, Site A might replace session 8 with PARS but Site B might replace session 14, so baseline assessments will be conducted in week 7 at Site A and week 13 at Site B. (Data collection methods for baseline assessments described in Procedures below.) This will assure that the follow-up assessments reflect the period after PARS is administered while allowing the natural variation in IOP curriculum that is inevitable with 15 community partner sites.

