Drug and alcohol use. To assess baseline substance use problems, participants will complete the Alcohol, Smoking and Substance Involvement Screening Test (ASSIST),⁴⁸ an 8-item screening tool developed by the World Health Organization to examine lifetime and recent (past three months) substance use, problems resulting from substance use, and risk of current or future harm from substance use. The ASSIST demonstrates acceptable to excellent test-retest reliability ($r = .58$ to $.90$), rater agreement (kappas = .61 to .78) and acceptability in substance users. To assess alcohol use problems at baseline, participants will also complete the Alcohol Use Disorders Identification Test (AUDIT) self-report,⁴⁹ a 10-item questionnaire that examines frequency, severity, and negative consequences of alcohol use. The AUDIT has demonstrated excellent internal consistency ($\alpha = .80$ to $.98$), sensitivity (.74 to .92) and specificity (.71 to .94) in detecting hazardous drinking and alcohol related problems (e.g., hospital admissions, social problems, outpatient treatment, medical disorders).⁴⁹⁻⁵¹ At each follow-up, participants will be asked to report on how many of the past 30 days they used drugs or alcohol.

Depression, Physical and Mental Health. Two screening measures will be used to assess covariates and potential moderators (depression, physical health, mental health) of PARS outcomes. The two-item Patient Health Questionnaire (PHQ-2)⁵²⁻⁵⁴ assesses recent depressive symptoms, and has excellent sensitivity (.77 to .86) and specificity (.78 to .95) in detecting major depression.^{52,53} The Short-Form 12 Health Survey (SF-12) consists of 12 items assessing overall physical and mental health, and demonstrates excellent test-retest reliability over two weeks ($r = .76$ to $.89$) and convergence with other health measures.⁵⁵

Treatment engagement will be measured by a combination of three metrics (a) % sessions attended, (b) graduated from program or terminated, and (c) clinician rating of participant's engagement in IOP treatment. Discharge plan for each client will be determined by a query of the IOP medical record as well as clinician report. (See PARS IOP Discharge Ratings in Appendix).

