Moderation Analyses. We will examine whether individual-level factors (e.g., demographic characteristics, drug and alcohol use, depression, physical and mental health functioning, treatment engagement) moderate the effect of the PARS program. To evaluate these individual-level moderators, the primary outcome analyses above will be extended to include the main effect of the moderator and its interactions with Treatment, Time, and the Treatment by Time interactions. Each moderator will first be evaluated in a separate model to ascertain whether any differences in treatment effects were associated with individual level factors. A follow-up model will evaluate the moderators simultaneously in a single model. The statistical test of moderation will be the three-way Treatment by Time by Moderator interactions.

[figure not shown]
Mediation Analyses. Secondary mediation analyses will examine whether baseline to post-intervention 1) increases in knowledge about suicide and 2) decreases in maladaptive attitudes about suicide will mediate the effect of PARS vs. TAU help-seeking behaviors. The mediation analyses will be conducted using multilevel structural equation modeling.⁶¹ Robust standard error estimates and corrected model fit statistics (e.g., Satorra-Bentler statistic) will be utilized to accommodate non-normally-distributed dependent variables in the model.⁶² Each mediator will first be evaluated in a separate model. Figure 2 illustrates the basic autoregressive regression model⁶³ that will be used to assess longitudinal mediation of the effect of intervention on 1-, 3-, and 6-month help-seeking behavior. An indicator variable for Step will be included as a covariate if the effect of step is statistically significant in the primary outcome analyses. The model will incorporate random effects for site and individual to account for the clustered design (i.e., repeated measures nested within individuals, nested within site). The mediated effect ($a_1 * b_5$) and its confidence interval will be obtained using bootstrap resampling, as recommended for testing indirect effects.⁶⁴ (Note, arrows on upper right side of mediator and outcome boxes represent error terms.)

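### Treatment engagement is measured partly after the PARS or TAU session, so its interaction with treatment cannot be read as effect modification

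*SAP*

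**What the plan says.** SAP C.7 (Moderation Analyses) tests individual-level factors one at a time and then together in a single model. The test is the three-way Treatment by Time by Moderator interaction. Engagement is in the list: "physical and mental health functioning, treatment engagement) moderate the effect of the PARS program".

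SAP C.5 (Measures) defines it: "Treatment engagement will be measured by a combination of three metrics (a) % sessions attended, (b) graduated from program or terminated". The third component is a clinician's rating of the client's engagement in the IOP. The next sentence, on discharge plans, points to a form: "See PARS IOP Discharge Ratings in Appendix". That appendix is not among the documents.

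Protocol 5.2 takes attendance and completion from the treatment record: "This will allow us to determine how many IOP sessions they attended and whether they completed the program".

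On timing, Protocol 5.1 says of the baseline assessment: "Will always occur one week prior to session intervention". The session sits inside the curriculum. SAP C3 gives the example "Site A might replace session 8 with PARS but Site B might replace session 14".

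The opening paragraph of SAP C.5 (Measures) has its own list of potential moderators: substance use, depression, health functioning and demographics. Engagement is not in it.

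**The concern.** A moderator should be fixed before treatment can act on it. Engagement as defined is not. If PARS keeps some clients in the program who would otherwise have left, the completers under PARS and the completers under TAU are different kinds of client. Comparing the conditions within completers, or within non-completers, is then no longer a comparison of like with like.

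The rating raises a second problem. SAP C3 states "The IOP counselor will administer PARS", and nothing says that the clinician who rates engagement is blind to condition. A rating made after the session may also partly reflect how the client responded.

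At stake is a secondary claim about who benefits from PARS. A difference between engagement groups could arise with no real effect modification, or a real one could be hidden. Because the plan also fits all moderators at once, the estimates for proper baseline moderators would be conditioned on a post-session variable.

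**Working it through.** The documents give no figure for the moderation analysis, so there is none to reproduce. The check has three parts.

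**1. Timing of each component against the session**

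| Component | Before the session | After the session |
|---|---|---|
| Share of sessions attended | sessions already attended | all later sessions |
| Graduated or terminated | – | settled here for clients who receive the session |
| Clinician rating | timing not stated | apparent link to discharge ratings |

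No passage in either document confines engagement to the period before the session, blinds the rating, or names a method for a post-randomisation variable. An IOP runs 8 to 12 weeks (SAP C3), so for some clients the 1-month outcome will be recorded before engagement is final.

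**2. Size of a false interaction in the planned model (all values assumed)**

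Let *U* be unmeasured motivation, standard normal. It affects the outcome by *g0* at baseline and *g1* at follow-up. The true PARS effect is 0.30 SD for everyone, so there is no moderation. Let *D* be the PARS minus TAU difference in mean *U* within an engagement stratum. SAP C.7 codes Time as contrasts against baseline, so the apparent effect in a stratum is

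0.30 + (*g1* − *g0*) × *D*,

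and the false interaction is (*g1* − *g0*) × (*D*engaged − *D*not engaged).

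Suppose PARS raises completion from 50% to 61%, only among less motivated clients. A simulation of 2 million clients, using follow-up alone with *g1* = 0.4, gives apparent effects of 0.31 (not engaged) and 0.21 (engaged). Hence:

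- *D*not engaged = (0.31 − 0.30) / 0.4 = 0.025
- *D*engaged = (0.21 − 0.30) / 0.4 = −0.225
- difference = −0.25

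| *g0* | *g1* | False interaction |
|---|---|---|
| 0.4 | 0.4 | 0 × (−0.25) = 0 |
| 0.2 | 0.4 | 0.2 × (−0.25) = −0.05 SD |
| 0 | 0.4 | 0.4 × (−0.25) = −0.10 SD |

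If completion rises from 50% to 71% instead, the corresponding values are 0, about −0.10 and −0.19 SD. If PARS shifts everyone's completion equally (50% to 69%), follow-up alone gives about 0.20 and 0.22 in the two strata. The change from baseline with *g0* = *g1* returns about 0.30 in both.

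**3. How often the test would mislead at N = 900**

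Assumptions: 1:1 split, independent clients, constant effect, follow-up outcome only, linear interaction test at two-sided 5%, 3,000 runs per scenario (simulation error about √(0.05 × 0.95 / 3000) = 0.4 points).

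| How engagement arises | False-positive rate |
|---|---|
| Fixed before the session | 4.8% |
| Uniform shift under PARS | 5.3% |
| Graduated yes/no, with a shift | 4.9% |
| Lift only in less motivated clients | 5.2% |
| Range compressed under PARS | 5.2% |
| Shift with a ceiling, as attendance can have | 13.1% |
| Rating tracks outcome more under PARS | 73.4% |

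Simple shifts leave the error rate near nominal. A ceiling raises it. A rating that follows the client's own outcome more closely under PARS raises it most. These rates come from a follow-up-only model and show the mechanism, not the error rate of the planned test.

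**The case against.** The strongest reply is that the planned test is not a comparison of follow-up scores within engagement groups. It uses change from baseline, and a stable trait that acts equally on both occasions cancels. This stands. A reader might infer from a follow-up-only calculation that PARS effects within engagement strata are biased whenever PARS changes engagement, even with no interaction. The documents do not support that: with *g0* = *g1* the strata return 0.30. Bias needs motivation to predict change, not only level. The cancellation is exact for a linear model; where the SAP's logit link is used it need not be.

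Other points also stand in part:

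- A reader might infer that all three components are fixed at the end of the IOP. Attendance also counts sessions before the PARS or TAU session, and the timing of the rating is not stated.
- Nothing in the documents shows that one session among 24 to 36 changes retention or ratings. The completion gains above are assumptions.
- A reader might expect the artefact to favour engaged clients. In the completion scenario it runs the other way.
- Distortion of the baseline moderators through the simultaneous model is possible but has not been quantified.
- Engagement is one item in a list of examples within a secondary analysis.

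None of this makes engagement a pre-treatment variable. The rating problem is also not removed by a baseline contrast, because a rating that reflects response to the session carries information that arises after baseline.

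**Conclusion.** The concern holds in a limited form. Engagement as defined can be affected by PARS, so its interaction with treatment cannot be interpreted as effect modification, whichever sign it takes. Its inclusion in the simultaneous model may also disturb the baseline moderators.

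The size is unknown from the documents. Under the assumptions shown, with completion rising from 50% to 61%, the false interaction runs from zero to about −0.10 SD, against a true constant effect of 0.30 SD. An unblinded rating that tracks outcome could do more. It would go too far to say that the moderation result will be an artefact; it could be one, and the planned analysis gives no way to tell.

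The primary Treatment by Time tests and the power statement do not depend on this. Severity is low to moderate.

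**What to change.** In SAP C.7, remove treatment engagement from the moderator list and from the simultaneous model. State that moderators are limited to variables fixed before the PARS or TAU session, which also brings the list into line with the one in C.5. Report end-of-program engagement descriptively as an outcome by condition.

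Attendance up to the baseline visit could replace it, but only if the treatment record gives dated attendance. Protocol 5.2 promises the number of sessions and completion, not dates. Entry to the IOP is rolling (Protocol 5.1), so this measure may carry little information for clients who joined shortly before baseline.

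Removal and descriptive reporting need only a change of SAP wording. The cost is the loss of end-of-program engagement as a moderator. The attendance option may need extra abstraction from the record.

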Given these promising Stage I results in Stage III settings, we propose a fully-powered Stage III effectiveness trial of PARS compared to Treatment-as-Usual (TAU) using a stepped wedge design with 900 clients enrolled in 15 community addiction treatment sites (see Figure 1 for design model). We will collect outcome data post-intervention and at 1, 3, and 6 months follow-up. We propose the following research aims:

Aim 1: Compare the effectiveness of IOP integrating PARS to TAU to change beliefs about suicide and suicide prevention.

Hypothesis 1a: Clients who receive PARS will know more accurate information about suicide

Hypothesis 1b: Clients who receive PARS will have less maladaptive attitudes about suicide

Aim 2: Compare the effectiveness of IOP integrating PARS to TAU to increase help-seeking behaviors for clients and for clients’ friends or family at risk of suicide.

Hypothesis 1c: Clients who receive PARS will show greater help-seeking for themselves and others

Aim 3: Evaluate whether changes in beliefs about suicide and suicide prevention—particularly regarding warning signs for suicide, including addiction, intoxication, and relapse, as well as beliefs that suicide is preventable when action is taken—are possible mechanisms by which PARS increases help-seeking behavior.

Hypothesis 2: The effect of PARS vs. TAU on changes in help-seeking will be mediated by improved information and attitudes

Exploratory Aim 4: Evaluate possible clinic-level dose effects of PARS administration such that participant outcomes improve the longer PARS is implemented within clinics.

Exploratory Aim 5: Compare the effects of PARS vs. TAU on clients’ suicidality *and* substance use in the follow-up period.

By integrating PARS into IOP group treatment, community treatment agencies are in a unique position to act as key players in the national suicide prevention strategy by providing suicide prevention information, improving attitudes regarding suicide, and increasing help-seeking skills for one of the most high-risk populations for suicide. This proposal is innovative in its focus, the development of PARS in community settings, as well as the use of a stepped wedge design.

A. Background and Significance

1. Suicidal behavior is prevalent and costly in substance-abusing populations.

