4. Explicit examination of treatment outcome mediators: Because the proposed research directly examines potential mediators of treatment effectiveness (i.e., accurate information and adaptive attitudes mediating improved help-seeking behavior), this study can guide future efforts to improve the PARS program. Identifying mechanisms of treatment action may allow us to refine PARS; making it more potent and targeted by increasing the emphasis on challenging maladaptive attitudes, increasing factual knowledge, or both.

5. Built-in counselor re-training: As noted above, PARS could represent an innovative training strategy for counselors who are consistently updated in these competencies by repeatedly using skills taught through PARS training with each new IOP group cohort. Few studies have examined the effects of repeated training exposure on suicide prevention effectiveness for clients, thus our exploratory aim examining dose effects may make an important contribution to this literature by testing whether there are effects of repeated exposure to PARS at the clinic level on client outcomes.

C. Approach

C.1. Preliminary Studies

R21 Preventing Addiction Related Suicide (PARS) study.

As part of a NIDA R21, a pre-post pilot study of PARS was conducted with clients attending group-based IOP addiction treatment at one of three publicly funded addiction treatment agencies in Washington State.¹ All agencies were members of the NIDA Clinical Trials Network (CTN) and were in urban areas. Prior to PARS, none of the agencies included a suicide module in their IOP programs (for more detail on IOP in Washington State, see Design section C.3). Seventy-nine clients were approached, of whom 78 consented to participate.

The inclusion criterion was current participation in IOP treatment. Exclusion from participation was based on the following criteria: (1) imminently suicidal patients as well as those who had planned or attempted suicide within the past 3 months, (2) patients with cognitive or language barriers judged severe enough to impede participation (no one was excluded on either criteria). Follow-up data were collected from 64 patients at the 1-month time point, for an 82% follow-up rate. Patients were given a \$25 gift card for completing each survey.

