Participants will be reimbursed (in a choice of gift cards) \$30 for their time for each baseline, \$20 for post-treatment, and follow-up assessments in increments of \$10 for each 10 questions completed. To minimize attrition, participants will also be offered an addition incentive to be paid at the final 6-month assessment (or end of the 6-month assessment window if they do not complete it). The additional incentive (also in gift cards) will be \$20 for completing 2 of the 3 outcome assessments and \$30 for completing all outcome assessments.

C.7. Data Analytic Plan

Data screening and preliminary analyses. First, exploratory data analysis will be performed to characterize the distributional characteristics of all variables. Frequency distributions and plots will be examined to identify out-of-range values and to assess data distributions. To assess scale reliability and validity, item structure will be examined using Cronbach's alpha and factor analysis. Descriptive statistics, stratified by site and study condition, will be examined to characterize sample characteristics and assess randomization. Baseline characteristics including socio-economic status, gender, suicidality, or substance use found to vary significantly between study conditions will be included as covariates in subsequent outcome analyses. Plots of mean outcomes by assessment point, site, and study condition will be examined to characterize outcome trajectories over time and inform the parameterization of time in the longitudinal models. Because differential attrition can compromise inference about experimental effects, we will compare dropouts and completers on demographic characteristics and available outcome variables.

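### The Aim 3 mediation text fixes no confounder set for the belief-to-help-seeking path and never states the joint model needed to separate knowledge from attitudes

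*SAP*

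**What the plan says.** SAP C.7, Mediation Analyses, asks whether baseline-to-post-session changes in knowledge and attitudes carry the effect of PARS on help-seeking. It uses multilevel structural equation modelling and a bootstrap interval for the product of two paths (a1 and b5).

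- **How the mediators enter:** "Each mediator will first be evaluated in a separate model". No second stage is described. The moderation paragraph just above also starts with separate models, but continues: "A follow-up model will evaluate the moderators simultaneously in a single model".
- **Covariates:** "An indicator variable for Step will be included as a covariate if the effect of step is statistically significant in the primary outcome analyses". No individual-level variable is named.
- **Structure:** "Figure 2 illustrates the basic autoregressive regression model", and "The model will incorporate random effects for site and individual to account for the clustered design". Figure 2 is not visible in the extract.
- **General covariate rule (C.7, data screening):** baseline characteristics, with suicidality and substance use among the examples, "found to vary significantly between study conditions will be included as covariates in subsequent outcome analyses".
- **Hypothesis 2:** "The effect of PARS vs. TAU on changes in help-seeking will be mediated by improved information and attitudes".
- **Intended use (SAP section B, item 4):** the result may help refine PARS, "making it more potent and targeted by increasing the emphasis on challenging maladaptive attitudes, increasing factual knowledge, or both".

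**The concern.** Sites are randomised to the step at which PARS starts, which protects the path from PARS to beliefs. Nobody is randomised to a level of knowledge or attitude after the session. The path from belief to help-seeking is therefore an observational regression and needs adjustment for common causes of the two. The general rule screens on difference between conditions, which is not the property that makes a variable a confounder of this path.

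Suicidality is the obvious candidate. One of the four help-seeking items asks whether the client sought help because of their own suicidal thoughts. SAP section A.2 puts ideation with a plan at 10% to 40% of clients entering addiction treatment, and C4 deliberately does not exclude them. That suicidality also shifts knowledge or attitudes is plausible but assumed. The bias could create apparent mediation or hide it.

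The second gap is separate. One session aims to move both beliefs, and they probably correlate. A model holding only one of them can credit it with the work of the other, and PARS could then be refined around the wrong belief.

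**Working it through.** **1. No plan figure to reproduce.** The documents give no effect size, sample size or power for mediation. The 89% and 80% power figures concern the month-1 help-seeking rate. Every coefficient below is an assumption.

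**2. Why balance is the wrong test.** Let S (suicidality) have the same distribution in both conditions, and let the belief M have no effect on help-seeking Y:

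- M = 0.5·PARS + 0.5·M0 + g·S + error (SD 0.8)
- Y = 0.3·PARS + 0.4·Y0 + d·S + error (SD 0.8)
- M0 and Y0 (baseline values, unit variance) load g and d on S.

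Regressing Y on M, PARS, M0 and Y0 gives a spurious path

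b = g·d·v / (g²·v + 0.64), with v = 1 / [1 + g²/(1−g²) + d²/(1−d²)].

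No difference in S between conditions enters this formula. For g = d = 0.2:

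- v = 1/(1 + 2 × 0.04/0.96) = 0.923.
- b = 0.0369/0.6769 = 0.0545 (simulated: 0.054).
- Without M0 and Y0 the simulated value is 0.087, so the autoregressive terms remove (0.087 − 0.054)/0.087 = 38% of the bias.
- At N = 900 the standard error is about 1/√900 = 0.033, so z is about 1.64 and b is significant in about 37% of trials (simulated: 39%).

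False mediation (both paths significant), 1,500 runs per setting, individual level, no clustering:

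| g = d | N = 900 | N = 675 | S adjusted, either N |
|---|---|---|---|
| 0.1 | 6% | 7% | 4–5% |
| 0.2 | 39% | 27% | 5% |
| 0.3 | 90% | 78% | 5% |

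**3. Sensitivity to how suicidality acts.** Three further sets of inputs, all with n = 720 (80% of 900) and with baseline belief and baseline help-seeking already adjusted:

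| Inputs | S omitted | S adjusted |
|---|---|---|
| 30% suicidal; PARS shifts belief 0.5 SD; S shifts belief 0.15–0.5 SD and help-seeking 15–25 points; linear models | 7–48% | about 5% |
| 15 sites, 6 steps, site and step effects, binary outcome near 15.6% | 6–20% | 5–7% |
| As the first row, but S shifts baseline and post-session belief alike (trait correlation 0.6) | 5% (0.15 SD, 15 points); 6.5% (0.25 SD, 25 points); 12% (0.5 SD, 25 points) | not run |

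The return to about 5% after adjustment holds by construction, because S is the only confounder simulated.

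**4. One belief or two.** Let knowledge be inert, attitudes have b = 0.3, PARS move both by 0.5, and their residual correlation be r. The separate knowledge model then estimates 0.3·r: 0.06, 0.12 and 0.18 at r = 0.2, 0.4 and 0.6 (simulated: 0.060, 0.120, 0.181). The joint model returns 0.000 to 0.001. At r = 0.4 the two separate indirect effects add to 0.5 × (0.12 + 0.30) = 0.21, against a true 0.5 × 0.30 = 0.15.

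Inert belief declared a mediator:

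| Setting | Separate | Joint |
|---|---|---|
| N = 900, r = 0 / 0.2 / 0.4 / 0.6 | 5 / 41 / 94 / 100% | 4–5% |
| N = 675, same r | 5 / 32 / 85 / 99% | 5–6% |
| n = 720, r = 0.3 / 0.5 / 0.7, linear models | 21 / 48 / 79% | 4–6% |
| n = 720, same r, 15-site layout, binary outcome | 26 / 57 / 82% | about 5% |

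In the last row the joint model still found the true mediator in 84% to 95% of trials. The first two rows assume a continuous outcome and a true effect of 0.3.

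**5. Price of the joint model.** The standard error of each belief's path grows by about 1/√(1 − r²): 1.05 at r = 0.3, 1.15 at 0.5, and 1/√0.51 = 1.40 at 0.7.

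**The case against.** A reader might infer that the plan leaves this path unadjusted, or that it has decided to analyse the beliefs only in isolation. The documents do not support either reading.

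- The paths and any covariates in Figure 2 cannot be seen, so only the text can be faulted.
- The word first implies a later model, the moderation paragraph supplies one after similar wording, and Hypothesis 2 names both beliefs. This looks like an unfinished specification.
- Adjustment is contemplated: C.7 lists suicidality as a candidate covariate, and the measures section describes the PHQ-2 and SF-12 as assessing covariates and moderators.
- An autoregressive model suggests that earlier values of belief and outcome are included, which removes part of the confounding.

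A reader might also take the high false-mediation rates as a forecast. They are not. They appear to need suicidality to move the post-session score beyond baseline, over about two weeks, and nothing in the documents shows that. The 15-to-25-point help-seeking shift is also generous. In the pilot, help-seeking for oneself rose only from 4% to 9%. If all of it fell in a 30% suicidal group, the gap would be 4/30 = 13 points before PARS and 9/30 = 30 after, about 22 on average. The friend and family items are endorsed more often (9% to 22%, and 9% to 17%).

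Finally, if one belief drives the other, a parallel model understates the upstream one, so it should not be the sole deciding analysis.

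All of this limits the size of the problem and the tone of the point. It does not rescue the covariate rule, which selects on the wrong criterion, and it does not supply the missing second stage.

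**Conclusion.** The point holds as a gap in prespecification. The mediation text names no confounder set for the belief-to-help-seeking path, and the general rule would bring in suicidality only on imbalance, which is irrelevant to bias in that path. The follow-up joint model is implied but never stated, so as written Aim 3 cannot tell knowledge from attitudes as section B intends.

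The size of the confounding bias is uncertain. It is negligible if suicidality acts weakly or as a stable trait captured by the baseline belief score, and substantial if it moves the post-session score beyond baseline. The joint-model gap is the firmer half: at correlations of 0.3 to 0.7, roughly 20% to 80% of simulated trials credited an inert belief, against about 5% jointly. More extreme inputs give higher rates. All of these figures rest on assumed coefficients, and most ignore clustering.

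The analysis is secondary and Aim 3 speaks only of possible mechanisms, so primary inference is untouched.

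**What to change.** Amend SAP C.7, Mediation Analyses:

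1. In both the mediator and the outcome equation, always include baseline suicidality, PHQ-2, substance-use severity, age and gender, whatever their balance, in addition to the baseline mediator and baseline help-seeking. Name the suicidality score: the SAP cites the SBQ-R, while Protocol 5.13 describes lifetime-history items at baseline, which may capture current suicidality only in part.
2. State the follow-up model with both mediators. Report it beside the two separate models, and base any statement about which belief carries the effect on it.
3. Keep Aim 3 conclusions at the level of possible mechanisms, since adjustment does not remove unmeasured confounding. A sensitivity analysis for such confounding would be a sensible addition.

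The cost is a few sentences and a few more parameters, because these variables are already planned for collection at baseline. The real price is precision: each belief's path has a standard error about 40% larger in the joint model if the beliefs correlate 0.7, and about 5% larger at 0.3.
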